10.3.1 Definition of AE

AE Definition

 • An AE is any untoward medical occurrence in a patient or clinical study

AE Definition

participant, temporally associated with the use of study intervention, whether or not considered related to the study intervention.

- Note: An AE can therefore be any unfavorable and unintended sign (including an abnormal laboratory finding), symptom, or disease (new or exacerbated) temporally associated with the use of study intervention.

Events Meeting the AE Definition

- Any abnormal laboratory test results (hematology, clinical chemistry, or urinalysis) or other safety assessments (e.g., electrocardiogram, radiological scans, vital signs measurements), including those that worsen from baseline, considered clinically significant in the medical and scientific judgment of the investigator (i.e., not related to progression of underlying disease).
 - Exacerbation of a chronic or intermittent pre-existing condition including either an increase in frequency and/or intensity of the condition.
 - New conditions detected or diagnosed after study intervention administration even though it may have been present before the start of the study.
 - Signs, symptoms, or the clinical sequelae of a suspected drug-drug interaction.
 - Signs, symptoms, or the clinical sequelae of a suspected overdose of either study intervention or a concomitant medication. Overdose per se will not be reported as an AE/SAE unless it is an intentional overdose taken with possible suicidal/self-harming intent. Such overdoses should be reported regardless of sequelae.
 - The signs, symptoms, and/or clinical sequelae resulting from lack of efficacy will be reported as an AE or SAE if they fulfil the definition of an AE or SAE. Also, “lack of efficacy” or “failure of expected pharmacological action” also constitutes an AE or SAE.

Events NOT Meeting the AE Definition

- Any clinically significant abnormal laboratory findings or other abnormal safety assessments which are associated with the underlying disease, unless judged by the investigator to be more severe than expected for the participant’s condition.
- The disease/disorder being studied or expected progression, signs, or symptoms of the disease/disorder being studied, unless more severe than expected for the participant’s condition.
- Medical or surgical procedure (e.g., endoscopy, appendectomy): the condition that leads to the procedure is the AE.
- Situations in which an untoward medical occurrence did not occur (social and/or convenience admission to a hospital).
- Anticipated day-to-day fluctuations of pre-existing disease(s) or condition(s) present or detected at the start of the study that do not worsen.

10.3.2 Definition of SAE

If an event is not an AE per definition above, then it cannot be an SAE even if serious conditions are met (e.g., hospitalization for signs/symptoms of the disease under study, death due to progression of disease).

An SAE is defined as any untoward medical occurrence that, at any dose:
a. Results in death
b. Is life-threatening The term 'life-threatening' in the definition of 'serious' refers to an event in which the participant was at risk of death at the time of the event. It does not refer to an event, which hypothetically might have caused death, if it were more severe.
c. Requires inpatient hospitalization or prolongation of existing hospitalization In general, hospitalization signifies that the participant has been detained (usually involving at least an overnight stay) at the hospital or emergency ward for observation and/or treatment that would not have been appropriate in the physician's office or outpatient setting. Complications that occur during hospitalization are AEs. If a complication prolongs hospitalization or fulfills any other serious criteria, the event is serious. When in doubt as to whether "hospitalization" occurred or was necessary, the AE should be considered serious. Hospitalization for elective treatment of a pre-existing condition that did not worsen from baseline is not considered an AE.
d. Results in persistent disability/incapacity 
 • The term disability means a substantial disruption of a person's ability to conduct normal life functions. • This definition is not intended to include experiences of relatively minor medical significance such as uncomplicated headache, nausea, vomiting, diarrhea, influenza, and accidental trauma (e.g., sprained ankle) which may interfere with or prevent everyday life functions but do not constitute a substantial disruption.
e. Is a congenital anomaly/birth defect
f. Other situations: 
 • Medical or scientific judgment should be exercised in deciding whether SAE reporting is appropriate in other situations such as important medical events that may not be immediately life-threatening or result in death or hospitalization but may jeopardize the participant or may require medical or surgical intervention to prevent one of the other outcomes listed in the above definition. These events should usually be considered serious. Examples of such events include invasive or malignant cancers, intensive treatment in an emergency room or at home for allergic bronchospasm, blood dyscrasias or convulsions that do not result in hospitalization, or development of drug dependency or drug abuse.

10.3.3 Recording and Follow-Up of AE and/or SAE

AE and SAE Recording

- When an AE/SAE occurs, it is the responsibility of the investigator to review all documentation (e.g., hospital progress notes, laboratory reports, and diagnostics reports) related to the event.
- The investigator will then record all relevant AE/SAE information in the CRF.
- It is **not** acceptable for the investigator to send photocopies of the participant's medical records to the sponsor in lieu of completion of the AE/SAE CRF page.
- There may be instances when copies of medical records for certain cases are requested by the sponsor. In this case, all participant identifiers, with the exception of the participant number, will be redacted on the copies of the medical records before submission to the sponsor.
- The investigator will attempt to establish a diagnosis of the event based on signs, symptoms, and/or other clinical information. Whenever possible, the diagnosis (not the individual signs/symptoms) will be documented as the AE/SAE.

Assessment of Intensity

All AEs will be coded using the Medical Dictionary for Regulatory Activities (MedDRA) coding system and graded using NCI-CTCAE version 5.0.

An event is defined as 'serious' when it meets at least 1 of the predefined outcomes as described in the definition of an SAE, NOT when it is rated as severe.

Assessment of Causality

- The investigator is obligated to assess the relationship between study intervention and each occurrence of each AE/SAE.
- A "reasonable possibility" of a relationship conveys that there are facts, evidence, and/or arguments to suggest a causal relationship, rather than a relationship cannot be ruled out.
- The investigator will use clinical judgment to determine the relationship.
- Alternative causes, such as underlying disease(s), concomitant therapy, and other risk factors, as well as the temporal relationship of the event to study intervention administration will be considered and investigated.
- The investigator will also consult the IB and/or Product Information, for marketed products, in his/her assessment.
- For each AE/SAE, the investigator **must** document in the medical notes that he/she has reviewed the AE/SAE and has provided an assessment of causality.
- There may be situations in which an SAE has occurred and the investigator has minimal information to include in the initial report to the sponsor. However, **it is very important that the investigator always make an assessment of causality for every event before the initial transmission of the SAE data to the sponsor.**
- The investigator may change his/her opinion of causality in light of follow-up information and send an SAE follow-up report with the updated causality

Assessment of Causality

assessment.

- The causality assessment is one of the criteria used when determining regulatory reporting requirements.

Follow-up of AEs and SAEs

- The investigator is obligated to perform or arrange for the conduct of supplemental measurements and/or evaluations as medically indicated or as requested by the sponsor to elucidate the nature and/or causality of the AE or SAE as fully as possible. This may include additional laboratory tests or investigations, histopathological examinations, or consultation with other health care professionals.
- If a participant dies during participation in the study or during a recognized follow-up period, the investigator will provide the sponsor with a copy of any post-mortem findings including histopathology.
- New or updated information will be recorded in the originally completed CRF.
- The investigator will submit any updated SAE data to the sponsor within 24 hours of receipt of the information.

10.3.4 Reporting of SAEs**SAE Reporting to the Sponsor via an Electronic Data Collection Tool**

- The primary mechanism for reporting an SAE to the sponsor will be the electronic data collection tool.
- If the electronic system is unavailable, then the site will use the paper SAE data collection tool (see next section) in order to report the event within 24 hours.
- The site will enter the SAE data into the electronic system as soon as it becomes available.
- After the study is completed at a given site, the electronic data collection tool will be taken off-line to prevent the entry of new data or changes to existing data.
- If a site receives a report of a new SAE from a study participant or receives updated data on a previously reported SAE after the electronic data collection tool has been taken off-line, then the site can report this information on a paper SAE form (see next section) or to safety at the vendor by telephone.
- Contacts for SAE reporting can be found in the Investigator site file.

SAE Reporting to the Sponsor via Paper CRF

- Facsimile transmission of the SAE paper CRF is the preferred method to transmit this information to safety at the vendor.
- In rare circumstances and in the absence of facsimile equipment, notification by telephone is acceptable with a copy of the SAE data collection tool sent by overnight mail or courier service.
- Initial notification via telephone does not replace the need for the investigator to

SAE Reporting to the Sponsor via Paper CRF

complete and sign the SAE CRF pages within the designated reporting time frames.

- Contacts for SAE reporting can be found in the Investigator site file.

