8.2 Safety Assessments

Planned time points for all safety assessments are provided in the SoA in Section 1.3.

Safety assessments in this study are AEs, as recorded by the investigator. Descriptive summary tables will be presented for all safety parameters by each treatment arm.

All AEs will be coded using the Medical Dictionary for Regulatory Activities (MedDRA) coding system and graded using NCI-CTCAE version 5.0. A TEAE is defined as any event arising or worsening after start of study drug administration until 30 days after the last study drug intake.

Fatigue, cognitive function and depression will be assessed as described below.

Other AEs of interest including fractures, falls, fractures, and hypothyroidism will be collected with specific questions on CRF.

Study assessments for physical ability and cognitive function are described in [Table 8–1](#).

Table 8–1: Study Assessments for Physical Ability and Cognitive Function

Test	Description	Possible range of score	MCID / RCI from baseline
Physical ability tests			
Timed Up & Go (TUG)	The TUG test is used to assess a person's mobility and requires both static and dynamic balance. It uses the time that a person takes to rise from a chair, walk three meters, turn around, walk back to the chair, and sit down. Where possible, TUG time is to be measured by independent blinded assessors.	>1second	1 second (Davies et al. 2016)
Short Physical Performance Battery (SPPB)	The SPPB is a group of measures that combines the results of the gait speed, chair stand and balance tests.	0–12 points	0.5 points (Davies et al. 2016)
Cognitive Tests			
Hopkins Verbal Learning Test-Revised Total Recall (HVLTR TR)	The HVLTR is a learning and memory test, in which the participant is asked to learn and recall a list of 12 words over 3 trials.	0–36 words	±5 words (Wefel et al. 2011)
Hopkins Verbal Learning Test-Revised Delayed Recall (HVLTR DR)	Spontaneous recall is assessed before and after a delay.	0–12 words	±3 words (Wefel et al. 2011)
Hopkins Verbal Learning Test-Revised Delayed Recognition (HVLTR RECOG)	Recognition discriminability is also assessed after a delay. Four alternate versions of the test are used to minimize practice effects over time.	-12–+12 words	±2 words (Wefel et al. 2011)

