	
  
 Test	Reliable Change Index threshold (from baseline)	
   
 Hopkins Verbal Learning Test - Revised Total Recall (HVLTR TR)	±5 words	
 
 Hopkins Verbal Learning Test - Revised Delayed Recall (HVLTR DR)	±3 words	
 
 Hopkins Verbal Learning Test - Revised Delayed Recognition (HVLTR RECOG)	±2 words	
 
 Trail Making Test: Part A (TMTA)	±12 seconds	
 
 Trail Making Test: Part B (TMTB)	±26 seconds	
 
 Controlled Oral Word Association (COWA)	±12 words	
  
 
 • The proportion of participants with a decline of >10 points from baseline in the FACT-Cog domain by 24 and 52 weeks will be summarized. 
Fatigue
 
 • The proportion of participants with an increase of at least 1 point in worst level of fatigue from baseline during the past 24 hours (item 3 of BFI) by 24 and 52 weeks will be summarized. • Similarly, the proportion of participants with an increase of at least 1 point in in fatigue interference from baseline during the past 24 hours (items 4A through F of BFI) by 24 and 52 weeks will be summarized. The proportion of participants with a decline and the 95% CIs will be summarized for each treatment arm. This rate will be compared between the two arms using Cochran-Mantel-Haenszel test adjusting for stratification factors as captured by IWRS. 
Depression
 
 • The proportion of participants with a worsening of scores by PHQ-9 during the 24 and 52 week period from baseline will be summarized. Worsening is defined as an increase of at least 1 point in worst level of depression from baseline by 24 weeks and 52 weeks. 
AE, Exposure, other
 
 • AEs, drug-related AEs, and SAEs will be summarized by MedDRA coding system and NCI-CTCAE version 5.0 worst grade. • AE of interest (fall, fracture, hypothyroidism) will be summarized descriptively. • Time to deterioration of KPS will be calculated as the time from randomization (or time from first dose for participants in the lead-in phase) to the first date the participant had a decline in KPS score of at least 10 points. Data will be summarized using the Kaplan-Meier method. • Treatment exposure of the study intervention, including time on treatment and dose reductions, will be summarized. 		Test	Reliable Change Index threshold (from baseline)	Hopkins Verbal Learning Test - Revised Total Recall (HVLTR TR)	±5 words	Hopkins Verbal Learning Test - Revised Delayed Recall (HVLTR DR)	±3 words	Hopkins Verbal Learning Test - Revised Delayed Recognition (HVLTR RECOG)	±2 words	Trail Making Test: Part A (TMTA)	±12 seconds	Trail Making Test: Part B (TMTB)	±26 seconds	Controlled Oral Word Association (COWA)	±12 words

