## 5.5 Safety and Tolerability Analysis

Safety analyses are based on the Safety population. Descriptive statistics are used to summarize the safety parameters. Safety data including AEs, AESI, laboratory parameters, vital signs, exposure and KPS. The protocol schedule of events and windowing will be used for the applicable safety table assessments.

Endpoints measuring physical function, daily activity and cognitive function will also be performed on the Safety population.

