### 5.5.3 AE, Exposure and Other

- AEs, drug-related AEs, and SAEs will be summarized in number (%) of patients.
- AEs of interest (Bone fractures, Diabetes mellitus and hyperglycemia, Fall, Fatigue/ asthenic conditions, Weight loss, Interstitial lung disease, Rash, Seizure, Hypertension, Mental impairment disorders, Depressed mood disorders, Breast disorders/gynecomastia, Cardiac disorders, Coronary artery disorders, Cerebral ischaemia, Cerebral and intracranial hemorrhage) will be summarized descriptively.
- Time to deterioration of KPS will be calculated as the time from randomization (or time from first dose in the lead-in phase) to the first date the patient had a decline in KPS of at least 10 points. In the event of no deterioration of KPS, the time to deterioration of KPS will be censored at the last evaluable assessment. Time to deterioration of KPS will be analyzed and presented the same way as the time to PSA progression.
- Treatment exposure of the study intervention, including time on treatment and dose changes, will be summarized.

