#### 5.5.5 Adverse Events

A TEAE is defined as any event arising or worsening after first dose study drug until 30 days after last dose. If an AE occurs before the first dose of treatment it will be considered a non-treatment emergent AE.

TEAEs and AEs will be summarized by frequency and percentage of patients and tabulated by MedDRA system organ class (SOC) and preferred term (PT), by maximum NCI-CTCAE version 5.0 grade and by drug relationship as not related and related to treatment. SAEs, TEAEs leading to treatment discontinuation and deaths will be summarized. Drug-related TEAEs by CTCAE grade, and drug-related grade 3 or higher TEAEs are summarized. Patients with multiple TEAEs or AEs are counted once within a summary category-SOC, PT, maximum grade, or relationship to treatments.

AESI be summarized by SOC and PT and grade in separate summary tables. All AEs will be listed.

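### No planned by-arm summary shows how many falls occurred or how many men fell repeatedly, because the SAP counts each man once per event term

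*Protocol*

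**What the plan says.** **Why falls matter here.** The protocol's rationale (1.1 and 2.1) names falls among the harms of AR inhibitors. Section 2.2 contrasts darolutamide with enzalutamide and apalutamide on falls. Section 3 lists falls among the AEs of interest under a safety objective that sets darolutamide against enzalutamide.

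**Collection.** Protocol 8.2: "Other AEs of interest including fractures, falls, fractures, and hypothyroidism will be collected with specific questions on CRF". Protocol 10.3.3, on causality: "The investigator is obligated to assess the relationship between study intervention and each occurrence of each AE/SAE".

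**Analysis.**
- Protocol 9.4.2: "AE of interest (fall, fracture, hypothyroidism) will be summarized descriptively".
- SAP 5.5: "Descriptive statistics are used to summarize the safety parameters".
- SAP 5.5.3: "AEs, drug-related AEs, and SAEs will be summarized in number (%) of patients". The same section lists fall and bone fractures among the AEs of interest.
- SAP 5.5.5: "Patients with multiple TEAEs or AEs are counted once within a summary category-SOC, PT, maximum grade, or relationship to treatments".
- SAP 5.5.5, for AEs of special interest: "AESI be summarized by SOC and PT and grade in separate summary tables".
- SAP 5.5.5, on listings: "All AEs will be listed".

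Neither document plans a total number of falls, a count of men who fell more than once, or a fall rate per unit of time. The SAP's index of outputs (section 9.0) covers the lead-in phase only and names no table for falls or other AEs of interest.

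**The concern.** A fall can recur in the same man, and the trial is about balance and mobility. A table that counts each man once per term shows how many men fell, but not how often. If one treatment raises the number of falls partly through repeat falls, the difference between arms looks smaller in the percentage of fallers than in the falls themselves. A reader of the study report would have to count falls by hand from the listings to see this. The gap does not depend on unequal follow-up: it is there even when both arms are observed for the same time.

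**Working it through.** **1. The counting rule.** SAP 5.5.3 sets the unit (patients) and SAP 5.5.5 sets the multiplicity rule (once per category). Together they give a man with five falls the same entry as a man with one. The separate tables for AEs of special interest add system organ class, preferred term and grade, but no event count.

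**2. The plan's own design figure.** It is used here only to fix the arm size. Protocol 9.2 assumes 20% vs 40% TUG worsening, 85% power, one-sided alpha 10% and 10% drop-out. With unpooled variance:

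n = (1.2816 + 1.0364)² × (0.2×0.8 + 0.4×0.6) / 0.2² = 5.373 × 0.40 / 0.04 = 53.7, so 54 per arm.

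2 × 54 / 0.9 = 120, which matches the plan. This point does not affect that figure. No design figure exists for falls.

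**3. What a once-per-man table shows.** Assumptions, none of them from the documents: one year of observation per man, and negative binomial falls with mean μ and dispersion k.

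P(any fall) = 1 − (1 + kμ)^(−1/k), which is μ/(1 + μ) when k = 1.

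Share of falls that are repeats = 1 − (sum of the two P) / (sum of the two μ).

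For k = 1:

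| Falls per man-year | True rate ratio | P(any fall) | Ratio seen in fallers | Repeat share |
|---|---|---|---|---|
| 0.05 vs 0.10 | 2.0 | 0.048 vs 0.091 | 1.91 | 8% |
| 0.10 vs 0.20 | 2.0 | 0.091 vs 0.167 | 1.83 | 14% |
| 0.25 vs 0.50 | 2.0 | 0.200 vs 0.333 | 1.67 | 29% |
| 0.20 vs 0.60 | 3.0 | 0.167 vs 0.375 | 2.25 | 32% |
| 0.30 vs 0.75 | 2.5 | 0.231 vs 0.429 | 1.86 | 37% |

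With the rate halved in one arm, 0.2 to 0.8 falls per man-year in the other, and k from 0 to 4, the repeat share runs from 8% to 57%.

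**4. The same loss expressed as power.** Simulated permutation tests, 54 men per arm, two-sided 5%, k = 1:

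| Falls per man-year | Any fall | All falls | Gain (points) |
|---|---|---|---|
| 0.25 vs 0.50 | 25% | 36% | 11 |
| 0.30 vs 0.75 | 54% | 72% | 18 |
| 0.20 vs 0.60 | 64% | 78% | 14 |

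Over k = 0.5 to 2 the gain in these three scenarios is about 10 to 21 points; an independent repeat gave about 8 to 20, a difference of the order of simulation error. At 0.10 vs 0.20 the gain is about 2 to 3 points, and at 0.05 vs 0.10 there is none.

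**5. Check by formula.** For 0.2 vs 0.4 falls per man-year and k = 1:

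- All falls: SE of the log rate ratio = √{[(1/0.4 + 1) + (1/0.2 + 1)] / 54} = √(9.5/54) = 0.419. Power = Φ(0.693/0.419 − 1.96) = Φ(−0.31) = 38%.
- Any fall: 0.167 vs 0.286, mean 0.226. Power = Φ[(0.119 − 1.96 × √(2 × 0.226 × 0.774 / 54)) / √((0.139 + 0.204) / 54)] = Φ[(0.119 − 0.158) / 0.0797] = Φ(−0.49) = 31%.

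The gain is 7 points. Over the grid in step 3 the formula gives gains of about 1 to 17 points: 26% vs 25% at 0.2 per man-year with k = 0, and 57% vs 40% at 0.8 with k = 1.

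**The case against.** - **A reader might infer that the repeat falls are thrown away.** The documents do not support that. SAP 5.5.5 lists all AEs and SAP 5.1 lists all raw data, so any fall recorded singly stays in the listings. It is missing only from the summaries.
- **A reader might infer that the counting rule is what stops falls being compared between arms.** It is not. Every AE of interest is descriptive in both documents, so even the percentage of men with any fall has no planned test. The power figures therefore compare two tests that the plan does not contain; they serve only as a measure of relative information.
- **A reader might take the causality rule in Protocol 10.3.3 as proof that each fall has its own dated record.** It is a general rule that does not mention falls. The same section prefers a diagnosis to its individual signs and symptoms, and the fall questions on the CRF are not in the documents. One yes/no question per visit would fit the text. This objection stands, and it makes the fix conditional.
- **The size depends on the assumed rates.** This stands too: at low fall rates the gain disappears.
- **Counting patients is a coherent way to describe safety, and the randomized phase is itself conditional on the lead-in results.** Both are true and keep the point minor. But a descriptive analysis does not require counting each man once, and a listing does not show whether repeat falls differ by arm.

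**Conclusion.** The point holds as a gap in the planned summaries: total falls, recurrent fallers and fall rates are not shown by arm for a harm that the protocol singles out. Severity is minor. The primary endpoint, sample size and type I error are untouched.

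The gain from counting every fall is illustrative: about 10 to 21 points of power when the higher-rate arm has 0.5 to 0.75 falls per man-year, about 2 to 3 points at 0.10 vs 0.20, and none at 0.05 vs 0.10. It rests on 54 men per arm, one year each, negative binomial counts and dispersion of about 0.5 to 2. None of the fall inputs is in the documents. That a large part of the information on falls is lost would be true only if falls are frequent or cluster in the same men, which the documents do not say.

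**What to change.** In SAP 5.5.3 and 5.5.5, for falls in the randomized phase, keep the percentage of patients and add one table by arm, labelled descriptive, with:

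- the total number of falls;
- the number of men with 0, 1 and 2 or more falls;
- falls per person-year over a common observation window: first dose to 30 days after last dose, cut at the final evaluation for both arms. The common cut matters because Protocol 4.4.2 ends data collection for enzalutamide at that point, while men on darolutamide may continue;
- a rate ratio with 95% CI from a negative binomial model, with log observed time as offset and the age stratum as covariate.

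If falls are too sparse for the model, give counts and crude rates only. For fractures, counts and crude rates are enough.

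First confirm that the AE or fall CRF page records each fall separately. If it does not, the table cannot be built from the planned data.

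Cost: one extra table. Visits, endpoints and sample size do not change. The downside is that a few frequent fallers can drive the rate ratio; the 0, 1 and 2-or-more counts beside it make that visible.
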